Chemistry panel for LFT investigations (local laboratory)	Includes GGT, chloride, bicarbonate, magnesium, and fractionated bilirubin. For subjects with AST, ALT, ALP or bilirubin Grade \geq 3, repeat chemistry panel and LFT investigations panel weekly until bilirubin with fractionation is $<$ 3x ULN, and AST, ALT and ALP is $<$ 5x ULN. Subjects with Grade 1 or Grade 2 elevations in AST, ALT, ALP or bilirubin at time of treatment discontinuation should continue to have tests monthly until resolution to at least baseline grade or until the start of subsequent therapy, whichever comes first.							If an adverse event of interest occurs
INR (or PT) and aPTT (local laboratory)	With additional assessments performed during treatment phase if subject has a hemorrhagic event.	X						Repeat during study if subject has a Grade \geq 3 bleeding event
Serum EPO level (local laboratory)	Only required during treatment at first suspected response. Repeat assessment is not required if response further improves.	X						At time of suspected HI-E (Hb), PR, CR

Table 3 Continued: Time and Events Schedule for Part 2, Main Study (Double-blind, Randomized 2:1, Imetelstat or Placebo Treatment)

Study Procedures	Comments	Screening Phase	Treatment Phase (4-week cycles \pm 3 days)					Posttreatment Follow-up Phase
		Up to 28 days before Randomization	Cycle 1 Day 1 (predose)	Cycle 1 Day 8, 15, 22	Cycle 2 Day 1, 8, 15, 22	Cycle 3 until EOT Day 1	EOT Visit 30 \pm 3 days after last dose	Survival Follow-up Every 12-16 weeks
Serum ferritin, transferrin saturation (local laboratory)	Total iron binding capacity and serum iron (Fe) may be performed to calculate transferrin saturation if transferrin saturation is not available at the site.	X	X		X (D1 only)	X	X	
B12 / folic acid / reticulocytes (local laboratory)		X						
Hepatitis serologies	Comprehensive hepatitis serology panel A through E. Hepatitis D serology is only required if the subject tests positive for the hepatitis B surface antigen (HBsAg). If the subject screening window is >28 days (Section 9.1.3), hepatitis screening results may still be used to determine eligibility outside of the initial 28-day screening period provided the subject is asymptomatic and does not meet Exclusion Criteria no. 12 (Section 4.2).	X						
Serum or urine pregnancy test		X			X (D1 only)	X	X	
Pharmacokinetics, Pharmacodynamics and Immunogenicity								

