The study drug may be held for up to 28 days from the expected start date of the scheduled cycle; a hold $>$ 28 days must be reviewed and approved by the sponsor. The study drug should be discontinued permanently if it cannot be restarted within 28 days due to toxicity. If the subject is exhibiting an otherwise positive clinical response to treatment and the toxicity appears to be manageable, contact the sponsor to discuss the specific case before study drug is discontinued.

Treatment During the Extension Phase

Dose modification guidelines provided in the following sections will continue in the Extension Phase. Subjects may receive treatment in the Extension Phase until there is loss of benefit or unacceptable toxicity, as determined by the investigator according to local standard of care.

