6.1.3. Dose Modifications for Liver Function Test Elevations and Hepatic Adverse Events

The actions in Table 10 should be taken for Grade 3 or 4 LFT elevations (AST, ALT and bilirubin), Grade 3 or 4 hepatic adverse events, and Grade ≥ 2 AST or ALT with Grade ≥ 2 bilirubin present at the planned start of a dosing cycle.

Table 10: Dose Modifications for Liver Function Test Elevations and Hepatic Adverse Events

Adverse Event	Action to be taken
Grade 3 or 4 AST, ALT, or bilirubin For ALT or AST $>8 \times ULN$ or baseline, contact sponsor and consider discontinuing drug altogether	
 • HOLD study drug and report as adverse event of interest (AEI) • Determine relatedness to study drug (i.e. extensive investigation^a to determine an alternative likely cause(s) for the event) 
 ○ If considered at least possibly related, after recovery to baseline, restart study drug at one dose level lower. ○ If not related, after recovery to baseline, restart study drug without dose reduction. • If the event recurs and is related, study drug should be discontinued

Adverse Event	Action to be taken
Grade 3 or 4 hepatic adverse event	
 • HOLD study drug and report as AEI • Determine relatedness to study drug (i.e. extensive investigation^a to determine an alternative likely cause(s) for the event) 
 ○ If considered at least possibly related, after recovery to baseline, restart study drug at one dose level lower. ○ If not related, after recovery to baseline, restart study drug without dose reduction. • If the event recurs and is related, study drug should be discontinued
Grade \geq 2 AST or ALT with concomitant Grade \geq 2 bilirubin* *Subjects with Grade 2 bilirubin at study entry should have worsening bilirubin with concomitant Grade 2 AST or ALT elevation	
 • HOLD study drug and report as AEI • Determine relatedness to study drug (i.e. extensive investigation^a to determine an alternative likely cause(s) for the event) 
 ○ If considered at least possibly related, discontinue study drug ○ If not related, after recovery to baseline, study drug can be restarted at same dose 
 ▪ If upon rechallenge the event recurs, study drug should be discontinued

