^a Extensive investigation includes repeating liver enzyme and serum bilirubin tests with fractionation once or twice weekly until levels return to baseline. Obtain additional tests to evaluate liver function, as appropriate (i.e., INR, albumin). In addition, obtain a detailed history of symptoms, prior or concomitant disease, concomitant medications (including nonprescription herbal and dietary supplements), alcohol use, recreational drug use, special diets and environmental chemical agents. The following should be ruled out: acute viral hepatitis types A, B, C, D and E; autoimmune or alcoholic hepatitis; nonalcoholic steatohepatitis (NASH); hypoxic/ischemic hepatopathy; and biliary tract disease and may require gastroenterology and hepatology consultations. Consider hepatology (or gastroenterology) consultation. Document findings in the Imetelstat Questionnaire for Adverse Event of Interest eCRF.

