9.8. Safety Evaluations

All subjects who receive at least 1 dose of study drug will be considered evaluable for toxicity. Any clinically relevant changes occurring during the study must be recorded in the eCRF. Any clinically significant abnormalities persisting at the end of the study/early withdrawal will be followed by the investigator until resolution or until a clinically stable endpoint is reached. The study will include the following evaluations of safety and tolerability according to the time points provided in the Time and Events Schedule for Part 1 and Part 2 (Table 1 and Table 3, respectively).

Adverse Events

Adverse events will be reported by the subject (or, when appropriate, by a caregiver, surrogate, or the subject's legally acceptable representative) for the duration of the study. Adverse events will be followed by the investigator as specified in Section 12 Adverse Event Reporting. Adverse events will be reported and graded according to the National Cancer Institute Common Terminology Criteria for Adverse Events (NCI-CTCAE), Version 4.03.

Adverse Events of Interest (AEI)

Specific adverse events or groups of adverse events will be followed as part of standard safety monitoring activities by the sponsor. These events will be reported to the sponsor within 24 hours of awareness irrespective of seriousness (ie, serious and non-serious adverse events) following the procedure described in the protocol for serious adverse events and will require enhanced data collection. The Imetelstat Questionnaire for Adverse Events Of Interest eCRFs must be completed for each AEI. For this study the adverse events of special interest are:

- ALT Grade ≥ 3 (>5.0 x ULN)
- AST Grade ≥ 3 (>5.0 x ULN)

- Bilirubin Grade ≥ 3 (>3.0 x ULN)
- ALP Grade ≥ 3 (>5.0 x ULN)
- All hepatic adverse events
- ALT or AST Grade ≥ 2 (>3.0 x ULN) **WITH** Bilirubin Grade ≥ 2 (>2.0 x ULN)

For these events, laboratory assessments should be repeated once or twice weekly until bilirubin with fractionation return to baseline levels. Additionally, subjects with Grade 1 and Grade 2 treatment-emergent elevations in AST, ALT, ALP and bilirubin at the time of treatment discontinuation should continue to have laboratory assessments monthly until resolution to at least baseline or until the start of subsequent therapy, whichever comes first. All hepatic adverse events and LFT abnormalities will be reviewed by an Independent Hepatic Expert Committee, at least quarterly, and as needed.

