Response assessment	Per modified IWG 2006; see Attachment 5. Response assessments to be performed per local standard or investigator discretion. Note: CR, PR or mCR only to be assessed in subjects with >5% baseline bone marrow aspirate blasts			Every 12 weeks from C1D1 (\pm 1 week) up to week 72, then every 24 weeks until suspected PD					At suspected PD, if feasible
ECOG performance status	See Attachment 4		X	X		X (D1 only)	X	X	
Survival status and subsequent therapy	Survival status and subsequent therapy are planned to be collected at the EOT visit and throughout survival follow-up period at least every 12 to 16 weeks (data may be collected more frequently, if needed).							X	X
Clinical Laboratory Assessments									
Chemistry (local laboratory)	Screening tests should be performed within 14 days prior to Randomization. For C1D1, no need to repeat if Screening tests performed within 5 days. After C1D1, tests must be performed within 48h before the scheduled visit. Refer to Inclusion Criteria above for further details. Refer to Sections 9.8 and 9.8.1 for additional detail on required clinical laboratory testing.		X	X	X	X (D1 only)	X	X	
Chemistry panel for LFT investigations (local laboratory)	Includes GGT, chloride, bicarbonate, magnesium, and fractionated bilirubin. For subjects with AST, ALT, ALP or bilirubin Grade \geq 3, repeat chemistry panel and LFT investigations panel weekly until bilirubin with fractionation is <3x ULN, and AST, ALT and ALP is <5x ULN. Subjects with Grade 1 or Grade 2 elevations in AST, ALT, ALP or bilirubin at time of treatment discontinuation should continue to have tests monthly until resolution to at least baseline grade or until the start of subsequent therapy, whichever comes first.			If an adverse event of interest occurs					
INR (or PT) and aPTT (local laboratory)	With additional assessments performed during treatment phase if subject has a hemorrhagic event.		X	Repeat during study if subject has a Grade \geq 3 bleeding event					
Serum EPO level (local laboratory)			X	Repeat during study per local standard of care or investigator discretion.					

Table 14 Time and Events Schedule for Part 2 Ventricular Repolarization Substudy^a								
Study Procedures	PHASE Comments	Screening Phase Up to 28 days before Randomization	Treatment Phase (4-week cycles ±3 days)					Posttreatment Follow-up Phase Survival Follow-up Every 12-16 weeks

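### After a Grade 3 or higher liver test the protocol gives three different points at which repeat testing may stop, and two of them allow it to end while enzymes are still raised

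*Protocol*

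**What the plan says.** Four places in the current protocol bear on follow-up of a raised liver test.

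- **Tables 3, 5 and 14, liver panel row.** After Grade 3 or higher AST, ALT, ALP or bilirubin, the site must "repeat chemistry panel and LFT investigations panel weekly until bilirubin with fractionation is" below 3 x ULN and the three enzymes are below 5 x ULN. The same row adds a monthly rule, but only for "Subjects with Grade 1 or Grade 2 elevations in AST, ALT, ALP or bilirubin at time of treatment discontinuation". That rule ends at baseline grade or at the start of subsequent therapy.
- **Section 6.1.3, Table 10, footnote a.** "Extensive investigation includes repeating liver enzyme and serum bilirubin tests with fractionation once or twice weekly until levels return to baseline". The table applies to events present at the planned start of a dosing cycle. Its laboratory triggers are AST, ALT and bilirubin, not ALP.
- **Section 9.8.** For the listed events of interest, which include isolated ALT, AST or ALP of Grade 3 or higher, "laboratory assessments should be repeated once or twice weekly until bilirubin with fractionation return to baseline levels". No enzyme appears in the stop.
- **Section 6.1.3, Table 10, actions.** Drug is held. For a possibly related Grade 3 or 4 value the instruction is "after recovery to baseline, restart study drug at one dose level lower".

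The routine chemistry row of Table 3 refers to Sections 9.8 and 9.8.1 for detail. It does not rank the rules.

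**The concern.** One event should have one end point for follow-up. Here the schedule tables stop at the lower edge of Grade 3, the dose-modification footnote stops at baseline, and Section 9.8 stops on a different analyte from the one that may have triggered it. Sites often work from the schedule table, which has the shortest rule for a bilirubin event. For an isolated enzyme rise, Section 9.8 is shorter still.

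What is at stake is patient safety. Section 1.1.5.2.3 names liver test abnormalities and hepatic events as the adverse events of concern, and says that a relationship of severe hepatobiliary events to imetelstat cannot be excluded. If repeat testing ends with an enzyme at Grade 2, a second rise or the return to baseline may be seen later than footnote a intends. Efficacy estimates are not affected.

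**Working it through.** The plan states no figure to reproduce. The check sets the rules side by side, runs assumed cases through them, and then sizes the exposed group.

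**Rules side by side**

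| Place | Frequency | Enzyme stop | Bilirubin stop |
|---|---|---|---|
| Tables 3, 5, 14 | weekly | below 5 x ULN | below 3 x ULN |
| Table 10 footnote a | once or twice weekly | baseline | baseline |
| Section 9.8 | once or twice weekly | none | baseline |

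Section 9.8 puts Grade 3 at above 5 x ULN for the enzymes and above 3 x ULN for bilirubin, so the table stop means only that the value is no longer Grade 3.

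**Case A: isolated ALT at a planned dose (assumed values).** Baseline ALT is 1 x ULN. ALT is 6 x ULN on Day 1 and 4.5 x ULN on Day 8, with bilirubin at baseline throughout.
- Tables: 4.5 < 5, so weekly panels may end on Day 8.
- Section 9.8: the bilirubin condition is already met on Day 1.
- Footnote a: continue until ALT is back at 1 x ULN. Drug stays on hold until then.

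The same event has three different stops.

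**Case B: ALT 4 x ULN with bilirubin 2.5 x ULN, normal at entry.**
- Tables: 4 < 5 and 2.5 < 3, so the stop is met.
- Section 9.8: bilirubin is not at baseline, so testing continues.

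Only the tables release this subject.

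**Case C: mid-cycle Grade 3 ALT that is Grade 2 by the next planned dose, bilirubin at baseline.** Section 6 takes this event outside the dose-modification tables, so drug is not held and footnote a does not apply. The tables stop below 5 x ULN and the 9.8 stop is met at once. Chemistry is still due within 48 hours before the next scheduled visit.

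**Case D: isolated Grade 3 ALP.** Table 10 has no laboratory trigger for it. Footnote a applies only if it is reported as a Grade 3 or 4 hepatic adverse event. Otherwise the choice is between the tables and the bilirubin-only stop in 9.8.

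**Subjects exposed.** Inputs: 3 of 38 target-population subjects in Part 1 had Grade 3 liver test elevations (Section 1.1.5.2.3); 3 of 57 Part 1 subjects had increased liver enzymes of Grade 3 or higher (Section 1.1.5.2.2); 115 subjects are planned on imetelstat (Section 11.3). Exact (Clopper-Pearson) limits are the 0.025 quantile of Beta(x, n-x+1) and the 0.975 quantile of Beta(x+1, n-x).

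- 3/38 = 7.9%, limits 1.66% to 21.38%. Times 115: 9.1 (1.9 to 24.6), about 9 (2 to 25).
- 3/57 = 5.3%, limits 1.10% to 14.62%. Times 115: 6.1 (1.3 to 16.8), about 6 (1 to 17).

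These count subjects with the triggering event, not subjects whose monitoring would lapse.

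**Extra blood under an aligned rule.** Take the three weeks from Day 8 to Day 29 in Case A. Weekly tests inside it fall on Days 15 and 22, so 2. Twice weekly gives about 5. At 10 mL per chemistry sample (Table 12) this is 2 x 10 = 20 mL to 5 x 10 = 50 mL, or 20/569 = 3.5% to 50/569 = 8.8% of the planned Part 2 volume.

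**The case against.** The best defence is that these are minimum requirements. A site that follows the longest one satisfies all three, and restart already needs evidence of baseline. The amendment summaries also show the intent: Amendment 6 says 9.8 was updated to match 6.1.3, and Amendment 8 says the liver row comments in Tables 3 and 14 were edited to match 9.8. The 9.8 sentence reads as though words were dropped. Section 9.8.1 further asks that, for a laboratory abnormality reported as an adverse event, a value supporting recovery to Grade 1 or baseline be recorded. All this stands and limits the practical effect. It does not remove the conflict: the live texts differ, none is given precedence, and 9.8.1 sets no testing frequency.

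Four stronger readings are tempting but unsupported.

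- *The protocol permits a 21-day gap without liver tests during a hold.* In Case A, footnote a applies to that very event and requires testing. The gap arises only if the site overlooks it.
- *A subject with combined ALT and bilirubin elevation can drop out of repeat testing.* Case B shows that 9.8 still requires it.
- *Late detection of recovery forces permanent discontinuation.* Section 6 does say "The study drug may be held for up to 28 days from the expected start date of the scheduled cycle" and "The study drug should be discontinued permanently if it cannot be restarted within 28 days due to toxicity". It also provides for sponsor review and approval of longer holds, and for sponsor contact before stopping a responder with manageable toxicity.
- *Isolated enzyme rises are the common pattern, so 9.8 misses most events.* The 67% ALT and AST rates against 11% for bilirubin are Grade 1 or 2 findings in 9 MDS subjects, none of whom had a Grade 3 or 4 liver test. Among 33 myelofibrosis subjects in the same study there was no Grade 3 or higher AST or ALT; the Grade 3 events were 2 ALP and 1 bilirubin.

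**Conclusion.** The point holds as an inconsistency in safety monitoring that is wrong as written and minor to moderate in weight. Two of the three texts let repeat testing end with an enzyme still at Grade 2: the schedule tables for any of the four tests, and 9.8 for an isolated enzyme rise. If the event was present at a planned dose, that can happen while drug is held for recovery to baseline. There is no gap at a site that follows footnote a.

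About 9 of 115 imetelstat subjects (2 to 25) would have a triggering event at the 3/38 rate, or about 6 (1 to 17) at the 3/57 rate. This assumes that Part 1 rates carry over to Part 2. The protocol does not say which test was raised in the 3 of 38. All three elevations were reversible, and the hepatic committee judged none drug-related. The Extension Phase and the QTc substudy carry the same table wording but are not counted here. The primary analysis, sample size and SAP are unaffected.

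**What to change.** 1. **Section 9.8.** Make the stop depend on both liver enzymes and fractionated bilirubin having returned to baseline.
2. **Liver rows of Tables 3, 5 and 14.** Replace the 3 x and 5 x ULN stop for enzymes and bilirubin with: *liver enzymes and fractionated bilirubin once or twice weekly until back at baseline, per Section 9.8 and Table 10 footnote a; after treatment discontinuation, once values are Grade 1 or 2, the monthly rule in this row applies, to baseline grade or the start of subsequent therapy*.

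The second clause prevents a weekly and a monthly instruction from applying to the same subject in one cell. The other expanded-panel analytes (GGT, chloride, bicarbonate, magnesium) can keep the present stop. The Table 10 triggers, the event-of-interest thresholds and the SAP stay as they are.

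The cost is three table cells and one sentence. Measured against the schedule tables alone, slow recoverers give a few more 10 mL samples: about 20 to 50 mL over three weeks, and more if recovery takes longer. Where footnote a already applies, these draws are already required. Follow-up of an isolated ALP rise becomes longer than under any current laboratory rule.

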11.4. Efficacy Analyses (Part 2)	A description of efficacy analyses related to QUALMS was added.
Attachment 7; Attachment 8; Attachment 9	Attachment 7 (EQ-5D-5L) was updated. Attachments for QUALMS (Attachment 8) and PGIC (Attachment 9) were added.
Rationale: The flexibility to use peripheral blood instead of bone marrow aspirate for cytogenetic testing will allow cytogenetic testing to occur when bone marrow aspiration is clinically unfeasible. Bone marrow aspirate is preferred to peripheral blood for cytogenetic assessment. The same sample type should be collected at screening and subsequent time points, if possible, because changes in cytogenetic findings may result for a given subject when different sample types are used.	
Time and Events Schedule (Table 1, Table 2; BM aspirate for cytogenetics); 9.5 Biomarkers (Cytogenetic Analysis)	Guidance was provided for when bone marrow aspiration yields a dry tap. Peripheral blood can be submitted if bone marrow aspirate cannot be collected. A consistent type of sample (peripheral blood or bone marrow aspirate) should be used throughout the study.
Rationale: Clarification was added to aid interpretation of procedures, for consistency with other parts of the protocol, and to reflect experience gained during conduct of Part 1.	
Synopsis (Exploratory Objectives)	The list of exploratory objectives was aligned with Section 2.1, Objectives.
Synopsis (Overview of Study Design); 3.1. Overview of Study Design; 11.2. Subject Information	The definition of “Study Entry” was clarified for Part 1 and Part 2 of the study. Study Day 1 is equivalent to Study Entry and is defined as the day of the first dose for subjects enrolled in Part 1 and the day of randomization for subjects enrolled in Part 2. In Section 3.1, specific reference to Study Entry as the day of the first dose was deleted, as the text is not specific to Part 1.
Synopsis (Endpoints); 9.2.2. Secondary Endpoints	Secondary endpoints were revised as follows: “Rate and amount of transfusions” was revised to “amount and relative change in RBC transfusions,” and “dose of myeloid growth factors usage” was revised to “ duration of myeloid growth factors usage.”
Synopsis (Safety Evaluations); 3.1. Overview of Study Design; 11.11. Independent DMC; 16.1. Study Design Considerations	The independent DMC’s involvement in the study was extended to Part 1 in addition to Part 2.

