Pharmacokinetic/Immunogenicity samples	See Table 4, Part 2 PK Time and Events Schedule.		Refer to Table 4.					
TL	Collection of samples for TL assessments will be done at baseline (C1D1) only.		X (predose)					
TA, and hTERT	Collection of samples for TA and hTERT assessments will be done at C1D1 predose, 24h post-dose, C1D8, C2D1, C2D8.		X (predose and 24h post-dose)	X (at D8 only)	X (at D1 [predose] and D8 only)			
Bone Marrow								
BM aspirate for cytogenetics (central laboratory)	Baseline aspirate for cytogenetics should be obtained during screening and must be submitted to the central laboratory to confirm eligibility. If results are available from cytogenetic assessment within 12 weeks prior to Randomization, or if aspiration yields a dry tap, peripheral blood sample (instead of a bone marrow sample) may be submitted for central cytogenetic assessment at screening. Central or local cytogenetics may be used for eligibility and stratification purposes. After baseline, BM assessments may be performed with a window of \pm 7 days.	X			Aspirate is required for all subjects with baseline abnormalities every 24 weeks after C1D1, at the time of suspected PR, or CR and every 24 weeks thereafter up to and including suspected PD. Sample should be obtained at the time of suspected PD for all subjects irrespective of baseline status. Information will be provided to the sites on which subjects will need to have repeat BM aspirate samples.			
BM aspirate for RNA Seq or CyTOF (if feasible)	Samples must be submitted to the central lab for all subjects if collection of the sample is feasible. The baseline aspirate sample may be collected during Screening or before dosing on C1D1. After baseline, BM assessments can be performed with a window of \pm 7 days.		X		At time of suspected PR, CR, mCR, and PD			

Table 3 Continued: Time and Events Schedule for Part 2, Main Study (Double-blind, Randomized 2:1, Imetelstat or Placebo Treatment)

Study Procedures	Comments	PHASE	Screening Phase	Treatment Phase (4-week cycles \pm 3 days)				Posttreatment Follow-up Phase	
		Up to 28 days before Randomization	Cycle 1 Day 1 (predose)	Cycle 1 Day 8, 15, 22	Cycle 2 Day 1, 8, 15, 22	Cycle 3 Day 1 until EOT	EOT Visit 30 \pm 3 days after last dose	Survival Follow-up Every 12-16 weeks	
Biomarkers									
Mutation analysis			X	Every 12 weeks after C1D1, at time of suspected response HI-E(Hb), PR, mCR or CR and at time of PD					
Ongoing Subject Review									

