Bone marrow aspirate samples will be collected from all subjects as outlined in the Time and Events Schedules (Table 1 and Table 3) for karyotype analysis to characterize cytogenetics at screening to correlate with clinical response.

For subjects with a cytogenetic abnormality at baseline, follow up samples should be collected every 24 weeks after C1D1, at the time of suspected CR or PR and every 24 weeks thereafter up to and including PD to evaluate eradication or reduction of a pre-existing abnormality for assessing cytogenetic response. For subjects with a normal baseline cytogenetic result, a sample should be collected at disease progression to evaluate appearance of a new abnormality for assessing possible mechanisms of progression. Peripheral blood may be submitted in place of an aspirate only if a bone marrow aspirate cannot be obtained (eg, dry tap). The same sample type collected at screening must be collected throughout the subject's participation in the study when possible. Sites will be provided with the baseline result report to determine what follow up samples should be collected.

Bone marrow sampling for cytogenetics on treatment is not required for subjects participating in the Ventricular Repolarization substudy (after Protocol Amendment 7).

Bone marrow aspirate for RNA Seq or CyTOF:

If sufficient sample is obtained, bone marrow aspirates may be characterized by technologies such as quantitative real-time polymerase chain reaction (qRT-PCR), gene expression profiling, microRNA, methylation, mutation, RNA sequencing and CyTOF analyses or other similar technologies utilized for analysis of RNA expression or proteins. Bone marrow sampling for RNA Seq or CyTOF is not required for subjects participating in the Ventricular Repolarization substudy (after Protocol Amendment 7).

Stopping Analysis

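### Table 3 and Section 9.5 of the protocol disagree on when blood may replace marrow for the baseline karyotype, so cytogenetic response can end up comparing blood with marrow

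*Protocol*

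**What the plan says.** Four places in the current protocol govern the karyotype sample in the main study of Part 2.

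- **Table 3, row on marrow aspirate for cytogenetics, screening.** The baseline aspirate is to go to the central laboratory. The row then gives two alternative triggers for blood, a cytogenetic result from the 12 weeks before randomization or a dry tap; under either, a "peripheral blood sample (instead of a bone marrow sample) may be submitted for central cytogenetic assessment at screening". The next sentence lets either central or local cytogenetics serve eligibility and stratification.
- **Table 3, same row, follow-up.** "Aspirate is required for all subjects with baseline abnormalities every 24 weeks after C1D1", and also at suspected PR or CR and up to suspected progression. No blood alternative is stated. Sites will be told which subjects need repeat aspirates.
- **Section 9.5, Cytogenetic Analysis.** "Peripheral blood may be submitted in place of an aspirate only if a bone marrow aspirate cannot be obtained". It adds: "The same sample type collected at screening must be collected throughout" the subject's participation, qualified as applying where possible. Follow-up samples in subjects with a baseline abnormality are taken "to evaluate eradication or reduction of a pre-existing abnormality for assessing cytogenetic response". Subjects with a normal baseline are sampled only at progression, to look for a new abnormality.
- **Attachment 5.** Complete cytogenetic response is disappearance of the abnormality with no new one; partial response is a reduction of at least 50%.

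Sections 3.2 and 9.3.1.3 describe the karyotyping as done on bone marrow. Section 9.2.3 and SAP 3.2.3 list cytogenetic change as exploratory. Section 11.13 has the Independent Review Committee (IRC) adjudicate cytogenetic response. The SAP does not mention sample type.

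**The concern.** Cytogenetic response is a within-subject comparison, so its meaning depends on baseline and follow-up being measured in the same tissue. The sponsor recognised this: the Amendment 1 rationale for allowing blood notes that "changes in cytogenetic findings may result for a given subject when different sample types are used", and the same-type rule in Section 9.5 carries that caution into current text. Table 3's first trigger works against it, because it allows a blood baseline in a subject from whom marrow could be obtained and then requires marrow afterwards.

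At stake is whether a recorded cytogenetic response, a missed response or a new abnormality reflects the disease or only a change of sample. Committee review does not remove the difficulty, since an adjudicator given one blood and one marrow karyotype cannot tell the two explanations apart.

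**Working it through.** No figure in the plan bears on this point, so the check is a comparison of the instructions.

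| Situation | Table 3 | Section 9.5 |
|---|---|---|
| Baseline, recent cytogenetic result exists, marrow obtainable | Blood allowed | Blood not allowed |
| Baseline, dry tap | Blood allowed | Blood allowed |
| Follow-up after a blood baseline, marrow obtainable | Marrow required | Same-type rule points to blood; only-if rule points to marrow |
| Follow-up after a marrow baseline, dry tap | Not addressed | Blood allowed |

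The conflict at baseline lies in the first row. The third row shows that Section 9.5 does not settle follow-up once blood has been sent: its two rules point to different tissues.

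Three paths follow.

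1. **Recent result exists, central blood is sent and is abnormal.** Table 3 calls for marrow every 24 weeks. Response is then a blood-to-marrow comparison. A 50% reduction would be taken between proportions measured in different tissues, and an abnormality seen only in marrow could count as new and block a complete response.
2. **Recent result is abnormal, central blood is normal.** Scheduled on-treatment karyotyping depends on having a baseline abnormality. Table 3 says sites will be informed and Section 9.5 says they receive the baseline report, but neither says which result governs. If the blood result governed, the subject would be sampled only at progression, and an abnormality already known from the earlier result could be recorded as new. If the earlier result governed, the subject would be resampled on treatment. The documents leave this open.
3. **Marrow baseline, dry tap at follow-up.** Section 9.5 itself allows blood here, so a mixed pair can arise even after Table 3 is corrected. Reconciling the two passages is therefore not enough; an analysis rule is needed as well.

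The SAP sections where such a rule would be expected (3.1 on the IRC, 3.2.3 on exploratory endpoints, 4.11.5 on biomarkers) contain none.

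**The case against.** The strongest case on the other side is that this is a wording inconsistency with small consequences. Cytogenetic response is exploratory and outside the primary test and the gate-kept sequence (SAP 4.9.1.3). The baseline sample is taken before randomization and the rule is the same in both blinded arms. The same-type rule in Section 9.5 applies only where possible, so its clash with Table 3 at follow-up is softer than a flat contradiction. The IRC charter and the possible separate biomarker SAP are not available here and may already deal with mixed pairs. A strict bar on blood could also force a repeat aspirate if no marrow is left to send. All of this stands. It limits the importance of the point and the form of the fix, but does not reconcile the two passages.

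A reader might infer more than the documents support:

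- **That a blood karyotype could distort IPSS stratification or admit ineligible subjects.** Table 3 lets local or central cytogenetics serve both purposes, and under the disputed trigger a recent result exists by definition.
- **That evidence of disease modification is at risk.** Section 3.2 uses that idea alongside CR, PR and mCR and about an earlier study; it does not tie it to cytogenetic response.
- **That blood would miss clones in a countable number of subjects.** The documents give no sensitivity for blood, no share of abnormal karyotypes and no share using blood. Low blood blasts in Attachment 1 do not supply the first of these.

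**Conclusion.** The conflict is real and lies in current text. Following Table 3 can produce a blood baseline with marrow follow-up for an endpoint defined by change from the subject's own baseline, and this SAP does not say how to classify such a pair. It is also unclear which baseline result decides who is karyotyped on treatment when a recent result and the central blood result differ.

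Neither the size nor the direction of the effect can be computed. The conclusion rests on two things: that at least some sites use the first trigger, and that findings can differ by sample type, which the sponsor itself states. It does not depend on blood being less sensitive than marrow. The primary endpoint and the gate-kept secondary endpoints are untouched. The point merits correction because the endpoint is adjudicated and the remedy is small.

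**What to change.** 1. **Protocol.** Reconcile Table 3 with Section 9.5 so that both give the same condition for blood at screening and the same tissue at follow-up. Where a marrow karyotype from the previous 12 weeks exists, use it as the response baseline and to decide who is resampled, with the tissue documented as marrow and the laboratory recorded as local or central. Require no repeat aspirate for this purpose.
2. **SAP, and the IRC charter if it has no such rule.** Call cytogenetic response, or a new abnormality, only when baseline and follow-up are the same sample type. List mixed pairs as not evaluable, by arm. Settle this before Part 2 is unblinded, as SAP 4.5 already requires for decisions to exclude data.

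For subjects whose baseline has already been taken, the table edit cannot change the sample; the existing marrow result and the analysis rule do the work.

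The cost is a table edit and a sentence or two in the SAP and charter. A few subjects become not evaluable for an exploratory endpoint, and some baselines will come from a local laboratory while follow-up is central, which is why the laboratory should be recorded. Table 3 does not say that the recent result came from marrow; where it did not, or the tissue is undocumented, the baseline substitution is unavailable and the same-tissue rule alone applies.
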